3.2.1.2 Titration Guidelines for the Optional Tolvaptan Treatment Component

In the optional tolvaptan treatment component of the trial, eligible subjects will receive tolvaptan based on age, weight, and the use of CYP3A4 inhibitors. Tolvaptan tablets will be administered orally QD, preferably in the morning hours.

Tolvaptan doses can be titrated QD and will be based on serum sodium levels assessed at 24 (\pm 4) hours following initiation of therapy and each subsequent dose. Titration guidelines are detailed in [Figure 3.2.1.2-1](#). Titration must occur in a hospital setting. Titration may not occur within 24 (\pm 4) hours of the previous dose and must be based on serum sodium assessment obtained $>$ 20 hours post previous dose. Titration is limited to no more than twice the previous dose, and will be limited to the maximum dose per body weight.

An age-appropriate formulation is not available for this trial. Therefore, the following subjects will be excluded from the optional treatment component of this protocol:

- Subjects $<$ 4 years of age, or weighing $<$ 10 kg,
- Subjects with an inability to swallow tablets, and
- Subjects weighing $<$ 20 kg and taking a moderate or potent CYP3A4 inhibitor

[Table 3.2.1.2-1](#) outlines starting tolvaptan doses and adjustments when tolvaptan is administered concurrently with potent or moderate CYP3A inhibitors. Tolvaptan doses will be reduced 75% and 50% if a potent or moderate inhibitor, respectively, is being concurrently administered.

Table 3.2.1.2-1 Starting Tolvaptan Doses With or Without Potent or Moderate CYP3A4 Inhibitors				
Age/Weight	Can subject swallow a tablet?	Starting Dose: No CYP Inhibitor	Starting Dose: Moderate CYP Inhibitor	Starting Dose: Potent CYP Inhibitor
≥ 4 y AND ≥ 10 to < 20 kg	Yes	3.75 mg	Not eligible for treatment	Not eligible for treatment
≥ 4 y AND ≥ 20 to ≤ 50 kg	Yes	7.5 mg	3.75 mg	Not eligible for treatment
≥ 4 y AND > 50 kg	Yes	15 mg	7.5 mg	3.75 mg

Based on the weight versus dose information provided in [Table 2.2-1](#) and taking into consideration the concomitant use of a CYP3A4 inhibitor, the starting doses are as follows:

Subjects ≥ 4 years of age and weighing ≥ 10 to < 20 kg:

- Not taking a moderate or potent CYP3A4 inhibitor will receive a QD oral tolvaptan tablet dose of 3.75 mg, with possible up-titration to 7.5 mg and 15 mg
- Taking a moderate or potent CYP3A4 inhibitor are not eligible for optional tolvaptan treatment

Subjects weighing ≥ 20 to ≤ 50 kg:

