- If the serum sodium level increases $>$ 4 to \leq 8 mEq/L (mmol/L)/24 hours in response to tolvaptan treatment and the serum sodium is \leq 140 mEq/L (mmol/L), then the dose of tolvaptan should remain the same for the subsequent day.
- If the serum sodium level increases $>$ 8 mEq/L (mmol/L)/24 hours or reaches a concentration of $>$ 140 mEq/L (mmol/L), then the next dose of tolvaptan should not be given and the medical monitor should be contacted to consider options (ie, down-titration, tolvaptan discontinuation, concomitant medication adjustment, fluid supplementation and/or withdrawal).
- If serum sodium level increases by \geq 12 mEq/L (mmol/L) in the 24 hour period following dosing, or, at any time after dosing, the serum sodium level is $>$ 145 mEq/L (mmol/L), the next dose of tolvaptan should not be given and the medical monitor should be contacted immediately to consider options.

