- 3) In addition to serum sodium samples obtained for treatment qualification and efficacy endpoints, supplemental samples for the purposes of safety assessment only will be obtained using a POC sodium assessment unit, where available, on Day 1 at 4 to 6 (+0.25) hours postdose and at 18 (\pm 1) hours postdose. A POC assessment unit is preferred; however, regular blood draws may be used (especially if they can be combined with standard of care labs).
- 4) Tolvaptan will be administered.

- 5) A blood sample for serum sodium testing will be collected 8 (-1 to +0.25) hours post-first dose.
- 6) Concomitant medications will be recorded.
- 7) Adverse events will be assessed.

[Table 3.7.4.1.2-1](#) presents the efficacy and safety serum sodium samples required during Day 1 of the titration period.

3.7.3.2.2 Day 2 up to Day 4

The investigator should schedule evaluations daily while the subject remains in a hospital setting per the schedule of assessments. The following procedures will be performed during the titration period:

- 1) Vital signs (blood pressure, heart rate, respiratory rate, and temperature) will be assessed after the subject has been supine for ≥ 3 minutes. Vital signs should be assessed prior to blood draws.
- 2) A blood sample for serum sodium testing must be assessed at 24 (± 4) hours post-dose (trough) on Days 2, 3, and 4. The results must be reviewed prior to tolvaptan dosing.
- 3) In addition to serum sodium samples obtained for treatment qualification and efficacy endpoints, supplemental samples for the purposes of safety assessment will be obtained using a POC sodium assessment unit, where available, at 6 (-1 to +0.25) hours postdose and at 18 (± 1) hours postdose on Days 2, 3, and 4 during the titration period. A POC assessment unit is preferred; however, regular blood draws may be used (especially if they can be combined with standard of care labs).
- 4) Administer tolvaptan. Tolvaptan will be titrated per the titration guidelines (see [Section 3.2.1.2](#)).
- 4) On Day 4, if a stable dose of tolvaptan has been confirmed, the initial titration phase will conclude, and sufficient tolvaptan will be dispensed for subjects that are outpatients for QD dosing until their next scheduled visit. Subjects and their parents/legal guardians will be instructed to return any remaining tolvaptan at the next visit for dose reconciliation.
- 6) Concomitant medications will be recorded.
- 7) Adverse events will be assessed.

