- 8) Instruct subjects not to take a tolvaptan dose before coming to the clinic for their Day 7 visit.

[Table 3.7.4.1.2-1](#) presents the efficacy and safety serum sodium samples required during Days 2, 3, and 4 of the titration period.

3.7.3.2.3 Days 7, 14, and 21

Subjects should arrive to the clinic prior to taking the morning dose of tolvaptan. The following assessments will be performed during each in-clinic visit during the first month of the treatment cycle:

- 1) Vital signs (blood pressure, heart rate, respiratory rate, and temperature) will be assessed after the subject has been supine for ≥ 3 minutes. Vital signs should be assessed prior to blood draws.
- 2) A blood sample for serum sodium testing must be assessed at 24 (± 4) hours post-last dose with the results reviewed prior to subsequent tolvaptan dosing.
- 3) Tolvaptan will be administered.
- 4) Tolvaptan dispensed at each visit will be returned for accountability.
- 5) Sufficient tolvaptan will be dispensed for subjects that are outpatients for QD dosing until their next scheduled visit. Subjects and their parents/legal guardians will be instructed to return any remaining tolvaptan at the next visit for dose reconciliation.
- 6) Concomitant medications will be recorded.
- 7) Adverse events will be assessed.
- 8) Instruct subjects not to take a tolvaptan dose before coming to the clinic for their Day 14, 21, and 30 visits.

Once the Day 30 visit is scheduled, the next visits (Days 31 to 34) must occur consecutively.

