- 3) A blood sample will be collected for serum sodium testing at 48 hours (± 4 hours) post the Day 30 dose. Refer to [Figure 3.1-1](#) for a trial schematic and [Section 3.2.1](#) for a description of the treatment continuation decision.
- 4) Concomitant medications will be recorded.
- 5) Adverse events will be assessed.

3.7.3.2.4.3 Day 33

The following assessments will be performed:

- 1) Vital signs (blood pressure, heart rate, respiratory rate, and temperature) will be assessed after the subject has been supine for ≥ 3 minutes. Vital signs should be assessed prior to blood draws.
- 2) A clinical status assessment will be performed. If the subject has any positive findings on the clinical status assessment, a full neurological examination can be performed per investigator judgment.

- 3) A urine or serum pregnancy test will be performed on female subjects ≥ 12 years of age and female subjects < 12 years of age if menstruation has started.
- 4) A blood sample will be collected for serum sodium testing at 72 hours (± 4 hours) post the Day 30 dose. Refer to [Figure 3.1-1](#) for a trial schematic and [Section 3.2.1](#) for a description of the treatment continuation decision.
- 5) Confirm need for continuing treatment.
 - a) If continuing treatment is needed and subjects have been off drug for < 72 hours:
 - Tolvaptan will be administered.
Subjects who reinitiate treatment at the same dose or a lower dose of tolvaptan after discontinuation for < 72 hours will not be required to reinitiate treatment in a hospital setting. However, tolvaptan will not be dispensed until subjects have a 24 hour postdose serum sodium assessment on Day 34.
 - b) If continuing treatment is needed and subjects have been off drug for ≥ 72 hours:
 - Subjects will reinitiate treatment, starting with titration ([Section 3.2.1.2](#)), which will require reassessment of the eligibility criteria. Titration will begin in a hospital setting as part of a new treatment cycle starting at the pretreatment baseline visit ([Section 3.7.3.2.1](#)). In these cases, the subject will re-start the schedule of assessments at the pretreatment baseline visit.
 - c) If no continuing treatment is needed:
 - The subject will move to the Follow-up Phase visit schedule and complete the assessments for the 7-day and 14-day post-last dose visits ([Section 3.7.3.2.7.2](#)).
- 6) Concomitant medications will be recorded.
- 7) Adverse events will be assessed.

3.7.3.2.4.4 Day 34

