3.7.4.1.2 Supplemental Sodium Samples for Safety

In addition to serum sodium samples obtained for treatment qualification and efficacy endpoints, supplemental samples for the purposes of safety assessment only will be obtained using a POC sodium assessment unit, where available. A POC assessment unit is preferred; however, regular blood draws may be used (especially if they can be combined with standard of care labs). The supplemental sodium samples for safety assessments are found in [Table 3.7.4.1.2-1](#).

Table 3.7.4.1.2-1 Serum Sodium Assessments During the Optional Tolvaptan Component				
Treatment Cycle	Phase	Day	Blood Draws for Serum Sodium	
			Efficacy	Supplemental Safety
Month 1	Pretreatment baseline	-4 to -1	Within 48 hours prior to tolvaptan administration, 2 blood samples, 12 hours apart	-
	Titration	1	2 to 4 hours prior to the first dose	-
			8 (-1 to + 0.25) hours postdose	4 to 6 (+ 0.25) hours postdose
		-	18 (± 1) hours postdose	
		2, 3, and 4	24 (± 4) hours post previous dose (trough)	6 (-1 to +0.25) hours and 18 (±1) hours postdose
Posttitration treatment	7, 14 and 21	24 (± 4) hours post previous dose	-	
Day 30 interruption		30	24 (± 4) hours post previous dose	-
		31	24 (± 4) hours post previous dose	
		32	48 (± 4) hours post previous dose	-
		33	72 (± 4) hours post previous dose	-
		34	24 (± 4) hours post previous dose	-
Month 2	Treatment	Every 14 (± 2) days	24 (± 4) hours post previous dose	-
Months 3, 4 and 5	Treatment (Maintenance)	Every month (± 2 days)	24 (± 4) hours post previous dose	-
Month 6/ET	Trial termination	-	Month 6 or trial termination	-
Follow-up	Follow-up	-	24 (± 4) hours post-previous dose	-
		-	7 (±1) days post last dose	-

Additional details can be found in [Section 3.7.3.2](#).

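### A dose raised on Day 4 has no scheduled 24-hour sodium, although titration is said to rest on one after each dose

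*Protocol*

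**What the plan says.** **Basis for titration (protocol 3.2.1.2).** Dose decisions rest on sodium at 24 (±4) "hours following initiation of therapy and each subsequent dose". Each change "must be based on serum sodium assessment obtained" more than 20 h after the previous dose, and may at most double it.

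**Hold rules (3.2.1.2).** If sodium rises by more than 8 mEq/L in 24 h, or exceeds 140 mEq/L, "then the next dose of tolvaptan should not be given and the medical monitor should be contacted to consider options". If it rises by 12 mEq/L or more in the 24 h after dosing, or exceeds 145 mEq/L at any time, the next dose is also withheld and the contact is immediate.

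**Titration days.** Table 3.7.2-1, footnote b, caps titration at 4 days. Section 3.7.3.2.2.2 covers Days 2 to 4 and includes among its procedures: "Tolvaptan will be titrated per the titration guidelines".

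**Sodium schedule.** Section 3.7.3.2.2.2 requires a sample at 24 (±4) "hours post-dose (trough) on Days 2, 3, and 4", reviewed before that day's dose. Table 3.7.4.1.2-1 times these samples from the previous dose. Supplemental safety samples follow the Day 2, 3 and 4 doses at 6 (-1 to +0.25) h and 18 (±1) h.

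**Leaving titration.** On Day 4, if a stable dose has been confirmed, titration ends and outpatients receive drug to take until the next visit. The last step reads: "Instruct subjects not to take a tolvaptan dose before coming to the clinic for their Day 7 visit". Section 3.7.3.2.3 then starts at Day 7.

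**Unscheduled sodium.** Section 3.7.4.1.3 allows it at the investigator's discretion but collects it only when linked to an adverse event. SAP 5.1.6.2 keeps unscheduled values out of the primary analysis.

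**The concern.** Day 4 is the last day on which a dose can be raised, and the raised dose may be twice the one before. Two of the four hold criteria use the change over 24 h, and section 5.3.1.1 defines rapid correction over the same period. If that 24-hour value is not scheduled after a Day 4 increase, the decision on the Day 5 dose rests on less information than the same decision on Days 2, 3 and 4. What is at stake is early recognition of overly rapid correction in children, which section 5.3.1.1 links to osmotic demyelination.

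**Working it through.** **1. Which doses have a 24-hour sample?** Assume once-daily dosing at a fixed clock time, so the Day d dose is given at hour 24 × (d − 1). The target window is then 20 to 28 h later.

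| Dose | Given at (h) | 24 (±4) h window (h) | Scheduled sodium in window |
|---|---|---|---|
| Day 1 | 0 | 20 to 28 | Day 2 trough |
| Day 2 | 24 | 44 to 52 | Day 3 trough |
| Day 3 | 48 | 68 to 76 | Day 4 trough |
| Day 4 | 72 | 92 to 100 | none |
| Day 5 | 96 | 116 to 124 | none |
| Day 6 | 120 | 140 to 148 | Day 7 trough |

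**2. What is scheduled after the Day 4 dose?**

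- First supplemental sample: 6 − 1 = 5 h to 6 + 0.25 = 6.25 h.
- Second supplemental sample: 18 − 1 = 17 h to 18 + 1 = 19 h. It ends 20 − 19 = 1 h before the window opens, and before the 20 h that section 3.2.1.2 requires for a titration decision.
- Day 7 trough: 140 − 72 = 68 h to 148 − 72 = 76 h.

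At nominal times the gap between samples is 72 − 18 = 54 h. The Day 5 and Day 6 doses fall inside it, so the Day 7 value reflects three doses at the new level (Days 4, 5 and 6).

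**3. Can an increase fall on Day 4?** Each eligible group in section 3.2.1.2 has two steps above the starting dose. With step-ups possible on Days 2, 3 and 4, and at most two of them, there are 2³ − 1 = 7 paths. Three include Day 4: Day 4 alone, Days 3 and 4, and Days 2 and 4. A child raised on both Day 2 and Day 3 is already at the top step. This count shows that the case can arise, not how often; the documents give no response rates from which to estimate that.

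**4. What can the 6 h and 18 h samples do?** Both come before a Day 5 dose at 24 h.

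| Criterion in 3.2.1.2 | Can it be met from these samples? |
|---|---|
| Level > 140 mEq/L | Yes |
| Level > 145 mEq/L at any time | Yes |
| Rise > 8 mEq/L in 24 h | Only if already exceeded when sampled |
| Rise ≥ 12 mEq/L in 24 h | Only if already reached when sampled |

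What stays unobserved is nominally the last 24 − 18 = 6 h after the Day 4 dose, then the response to the Day 5 and Day 6 doses until the Day 7 trough.

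**5. Does the stable-dose condition fill the gap?** The protocol does not define it by a sodium result. The synopsis equates it with not expecting to give a higher dose, and on that basis allows dosing outside hospital. There are two readings:

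- *No higher dose expected.* A child raised on Day 2 or 3 and again on Day 4 is at the top step, so the condition can be met on Day 4 itself. Drug may then be dispensed that day. With morning dosing, the 18 h sample falls overnight into Day 5, after dispensing.
- *Response must be seen first.* The child stays in hospital. Evaluations there are daily, but according to a schedule with no Day 5 or Day 6, and titration is capped at 4 days.

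Neither reading produces a scheduled 24-hour value.

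**The case against.** **The hold rules.** A reader might infer that they cannot be applied at all to a dose raised on Day 4. The documents do not support that. Two samples are required before the Day 5 dose. They can trigger both absolute limits and can reveal a rise that already exceeds 8 or 12 mEq/L. Section 3.8.3 adds triggers for confirmation and for contact with the medical monitor.

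**Home dosing.** A reader might also infer that a child whose dose was just doubled goes home unmonitored. The stable-dose condition stands in the way, and a dose doubled that morning is naturally read as not yet confirmed stable. That stands: the protocol does not direct such a discharge. It does leave the term open and says nothing about Day 5 if the condition fails.

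**The sentence in 3.2.1.2.** It says what titration decisions rest on, and every permitted decision, on Days 2, 3 and 4, has its trough. Read as a demand for a sodium after every dose, it would clash with the later weekly and monthly visits. That is fair, and the sentence is not a standing sampling rule. But the hold rules decide the dose that follows an increase, and after a Day 4 increase two of their criteria lack the scheduled value.

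**The Day 33 restart.** There, "tolvaptan will not be dispensed until subjects have a 24 hour postdose serum sodium assessment on Day 34". One might conclude that the protocol watches an unchanged dose more closely than a raised one. It does not follow: the Day 4 dose is given in hospital with two safety samples, whereas the Day 33 restart need not be in hospital and has none. The two kinds of monitoring differ and cannot be ranked.

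**Efficacy.** The primary analysis is descriptive and has no planned summary of the last titration step, so an efficacy consequence is not supported either.

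**Conclusion.** The point holds in bounded form. Section 3.2.1.2 and the sodium schedule do not meet for one dose: a dose changed on Day 4 has no scheduled sample between 19 h and 68 h. The 24-hour change behind the > 8 and ≥ 12 mEq/L rules is therefore unscheduled for it, while the level limits and early rises remain detectable. The stable-dose condition does not supply the missing value under either reading.

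This is a safety-related inconsistency that should be corrected, not evidence of harm. It touches only children whose dose changes on Day 4, and the documents do not allow that share to be estimated. The secondary endpoint on overly rapid correction is unaffected, because it concerns the 24 h after the first dose of a cycle, which the Day 2 trough covers. SAP 5.1 and 5.2 state that no subject received optional tolvaptan, so no analysed data change.

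The check assumes dosing at a fixed time of day. It rests on the text and on Table 3.7.4.1.2-1; the titration scheme in Figure 3.2.1.2-1 and the dosing and dispensing rows of Table 3.7.2-1 were not available to it and should be read alongside.

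**What to change.** Reconcile section 3.2.1.2, section 3.7.3.2.2.2, Table 3.7.2-1 and Table 3.7.4.1.2-1 so that they agree on:

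1. which sodium result governs a dose changed on Day 4;
2. whether drug may be dispensed before that result is reviewed;
3. what a confirmed stable dose means after a Day 4 change, and what is scheduled if the dose is not stable.

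The clinical answer to each belongs to the sponsor's clinicians. If the answer implies a further sample, list it in Table 3.7.4.1.2-1 as scheduled. Left to discretion, it would be collected only when linked to an adverse event.

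The cost is protocol wording, possibly one schedule column, and at most one further sodium in children whose dose changed on Day 4.

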3.2.2 Rescue Therapy

Rescue therapy is defined as any treatment, eg, hypertonic saline, isotonic saline (with or without diuretic for the purpose of increasing the serum sodium level), plasmapheresis/dialysis, demeclocycline, urea, lithium, or commercial vaptans intended to raise the level of serum sodium during the trial. Subjects who develop worsening hyponatremia symptoms may receive rescue therapy at any time during the trial. However, subjects who require rescue therapy during the optional treatment component will be discontinued from tolvaptan prior to receiving rescue therapy.

Subjects will continue to be followed per the schedule of assessments in the optional tolvaptan treatment component (Follow-up Phase visits). Treatment with tolvaptan may be reinitiated only per consultation with the medical monitor. Subjects who have received rescue therapy because of inadequate response to tolvaptan will not be allowed to reinitiate tolvaptan treatment.

For subjects participating in the optional tolvaptan component only, serum sodium values drawn up to, but not after, the initiation of rescue therapy will be included in the

calculation of the efficacy endpoint. Additional guidelines for rescue therapy concerning hyponatremia symptoms and decreasing serum sodium level are as follows:

- If a subject has worsening symptoms and/or has a serum sodium level at or below the baseline value for the current treatment cycle, repeat serum sodium immediately (STAT) to confirm level, and begin rescue therapy.
- If a subject is asymptomatic and serum sodium has decreased by ≥ 4 mEq/L (mmol/L), but is still above the baseline value, consider need for rescue therapy according to local standard of care.
- If a subject is asymptomatic and serum sodium has decreased by ≤ 3 mEq/L (mmol/L) but is still above the baseline value, no action is required.

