7.3 Handling of Missing Data

The primary dataset for efficacy analyses will be in the tolvaptan treated subjects - efficacy dataset. The efficacy dataset will consist of the actual observations recorded at each visit so that no imputation of missing values will be made.

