7.4 Primary and Secondary Outcome Analysis

7.4.1 Primary Outcome Analysis

The primary endpoint for all tolvaptan treated subjects is:

- Change from baseline in serum sodium while tolvaptan is being administered

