5.1.2 Handling of Missing Data

The primary dataset for efficacy analyses will be the observed cases (OC) dataset. The OC dataset will consist of the actual observations recorded at each visit so that no imputation of missing values will be made.

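### Rescue at or below cycle baseline, with later values excluded and nothing imputed, biases the observed-case mean sodium change upward in expectation from the second post-baseline assessment on

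*Protocol*

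**What the plan says.** Protocol 3.2.2 (Rescue Therapy) sends a child to rescue for worsening symptoms and/or when the child "has a serum sodium level at or below the baseline value for the current treatment cycle". The level is confirmed by an immediate repeat. Because symptoms and level are joined by and/or, a confirmed level is enough without symptoms. Such a child "will be discontinued from tolvaptan prior to receiving rescue therapy". On re-entry the section says: "Subjects who have received rescue therapy because of inadequate response to tolvaptan will not be allowed to reinitiate tolvaptan treatment". On the data it says: "serum sodium values drawn up to, but not after, the initiation of rescue therapy will be included".

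Protocol 7.4.1 defines the primary endpoint as "Change from baseline in serum sodium while tolvaptan is being administered", with no visit or estimator named. Protocol 7.3 limits the efficacy dataset to "actual observations recorded at each visit so that no imputation of missing values will be made". SAP 5.1.2 uses observed cases and repeats that "no imputation of missing values will be made".

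SAP 5.1.6.2 takes the last pre-dose sodium of each cycle as baseline and keeps unscheduled values out of the primary analysis. The SAP does not restate the rescue exclusion, but an endpoint restricted to time on tolvaptan has the same effect. The analysis is descriptive and there is no control group. The percentage needing rescue and the percentage with recurrent hyponatremia are separate secondary endpoints. SAP 5.1 records that no subject received optional tolvaptan.

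**The concern.** One number, the cycle baseline, is both the rescue threshold and the value subtracted to form the change score. A child whose change is confirmed at zero or less contributes that value and then leaves. The means at later visits are taken over children who have not yet met the rule, and they tilt towards high values whatever the drug does.

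The treatment component is meant to show that tolvaptan both achieves and maintains a higher sodium. An average that tends to climb over visits as low values leave it is weak evidence of maintenance. There is no control arm in which the same drift would show.

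**Working it through.** The plan gives no effect size, SD or rescue rate, so there is no stated figure to reproduce. The rule itself can be tested with a known true effect.

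**Inputs from the documents.** Rescue on a confirmed sodium at or below cycle baseline, tolvaptan stopped, later values excluded (Protocol 3.2.2). No imputation (Protocol 7.3, SAP 5.1.2). Baseline is one pre-dose value per cycle (SAP 5.1.6.2). Up to Day 30 there are eight scheduled on-treatment efficacy samples: Day 1 at 8 hours, then Days 2, 3, 4, 7, 14, 21 and 30 (Protocol Table 3.7.4.1.2-1).

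**Inputs assumed.** Between-child SD of the true change 2 to 3 mEq/L and within-child SD 1.5 to 2 mEq/L. The rescue rule is always followed.

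**Step 1, exact check of the direction.** Let an inert drug leave sodium varying independently around a constant child mean with SD s, with no confirmation step. A child is still observed at assessment k only if baseline was the lowest of the first k values (baseline plus k − 1 post-baseline values). Then

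P(still observed) = 1/k, and E[change] = −s × E[minimum of k standard normals].

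- k = 1: 0.00
- k = 2: 0.56s
- k = 4: 1.03s
- k = 8 (Day 30): 1.42s, with 1/8 = 12.5% of children left; for s = 2 this is +2.85 mEq/L

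The first assessment is unbiased because the triggering value is itself counted.

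**Step 2, simulation with confirmation.** Change = child effect + visit error, ten visits from Day 2 to Day 89. A child leaves when a visit value and its repeat are both at or below 0. The ranges cover the assumed SDs.

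| True mean change | Observed-case mean, Day 30 | Bias |
|---|---|---|
| 0 | +1.9 to +2.8 | +1.9 to +2.8 |
| +2 | +2.9 to +3.7 | +0.9 to +1.7 |
| +5 | +5.1 to +5.55 | +0.1 to +0.55 |

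For the inert drug the mean is 0.00 at Day 2 and +1.25 to +2.19 at Day 4. At Day 30, 34% to 41% of children remain, and 11% to 21% of the contributing values are still at or below baseline.

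**Step 3, sensitivity for the inert drug at Day 30.** With independent variation and s = 2, full adherence to the rescue rule gives +2.85 and half adherence gives +1.94. Serially correlated (AR(1)) sodium gives +2.88 and a random walk +3.22. Pooling all observed values to Day 30, instead of averaging by visit, still gives +0.6 to +1.8 for s from 1 to 3. The bias vanishes only if the baseline has no error or biological variation and later deviations are independent, which is implausible for a single sodium value.

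**Step 4, candidate corrections for the inert drug at Day 30.**
- Setting the change to 0 after rescue leaves (fraction remaining) × (their mean): roughly 0.34 × 1.9 = 0.65 to 0.41 × 2.8 = 1.15. Simulated directly it is about +0.7 to +1.1, so this is still biased upward.
- Carrying the triggering value forward gives about −0.3 to −0.8 in the Step 2 model. It gives 0.00 under a random walk and about −1.3 under independent variation with s = 2 and no confirmation. It is neutral or conservative.

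**The case against.** The endpoint is explicitly on-treatment. Values after rescue are off tolvaptan and contain the effect of rescue, so leaving them out of that endpoint is reasonable. This stands, and it is why the observed-case table should be kept.

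The bias is large mainly when the drug does little. Titration aims at rises of 4 to 8 mEq/L per 24 hours, and at a true change of +5 the bias is at most about 0.55. A weak drug would also show in the rescue and recurrence percentages. This also stands, but those percentages leave the primary mean unchanged, and no supporting analysis joins the two.

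The rescue rules are headed as guidelines, and Protocol 3.2.1.2 permits up-titration after a rise of 4 mEq/L or less while sodium is below 135. Some children might be titrated instead of rescued. Partial adherence lowers the bias without removing it.

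A reader might go further and infer that the mean is positive by construction, that the summary cannot show failure, or that only children above baseline are counted. The documents do not support this. Values up to the start of rescue count, so a triggering scheduled value enters at its own visit. A single unconfirmed low value does not remove a child. A sample mean can still be zero or negative.

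**Conclusion.** The point holds as a bias in expectation from the second post-baseline assessment on. The direction was upward in every plausible model run. The size rests on SDs that the documents do not give and on how closely the rescue rule is followed.

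The first post-baseline visit is unbiased unless an earlier sample triggers rescue. If the trigger falls on an unscheduled or supplemental safety sample, the low value never enters the endpoint, which adds to the bias.

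A reader might also infer that published efficacy results are inflated. They are not: SAP 5.1 says that no subject was treated and that these analyses will not be applied. The weakness is in the plan as written and matters if the wording is reused.

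**What to change.** Keep the observed-case on-treatment table. Add one supporting table over all treated subjects, by treatment cycle, with two summaries:

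- **Mean change.** For a child rescued or stopped for inadequate response, carry the last pre-rescue (triggering) sodium forward to the remaining scheduled visits. Use the triggering value even if it came from an unscheduled or supplemental sample. Do not set the change to 0.
- **Percentage above cycle baseline without rescue at each visit.** Count rescue, or stopping for inadequate response, as failure. Show separately the children whose treatment ended because it was no longer needed, so that successful short courses are not counted as failures.

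The cost is SAP wording and one table, with no extra visits or blood draws. Protocol 3.7.4.1.3 collects unscheduled sodium only when tied to an adverse event, so the plan should also ensure that the value that triggered rescue is recorded. The downside is a slightly conservative, less favourable mean.

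The overlap between the up-titration rule in Protocol 3.2.1.2 and the rescue guideline in 3.2.2 must be reconciled. No clinical rule is proposed here.
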